Study Sites (continued)	
Institute of Dermatology and Allergy Ludwig-Maximilians-Universität München [name] 80337 Munich, Germany
 
Department of Stomatognathic Function and Occlusal Reconstruction Institute of Biomedical Sciences Tokushima University Graduate School [name] 770-8504 Tokushima, Japan
 
Department of Dermatology, School of Medicine Faculty of Medicine, Toho University Toho University Omori Medical Center [name] Tokyo 143-8541 Japan

4.5 IRB/Ethics Committees	
Institutional Review Board National Jewish Health [name] Denver Colorado,80206
 
[name], Präsident EKNZ Ethikkommission Nordwest- und Zentralschweiz [name] 4056 Basel, Switzerland
 
Comitato Etico Ospedale San Raffaele [name] 20132 Milano, Italy
 
Medisch Ethische Toetsingscommissie VUmc [name] 1007 MB Amsterdam, Netherlands
 
Ethikkommission der Ludwig-Maximilians-Universität München [name] 80336 München, Germany

IRB/Ethics Committees (continued)	
Clinical Trial Center for Developmental Therapeutics Tokushima University Hospital [name] 770-8503 Tokushima, Japan [contact] [contact]
 
Toho University Omori Medical Center Institutional Review Board Toho University Omori Medical Center [name] Tokyo 143-8541 Japan

4.6 Objective	
To determine the optimal test allergen dose of metal allergens proposed for inclusion in Metal Panel T.R.U.E. TEST. The study will compare the diagnostic performance (primary endpoint) and safety (secondary endpoint) of ascending patch test doses of aluminum, copper, magnesium, molybdenum, tin, titanium, vanadium and zinc allergens.
 
To determine if subjects who have not had previous patch testing for contact metal allergy are allergic to any of the most common metal allergens; nickel, cobalt, chromium and gold.

4.7 Study Design	
This is a prospective, multi-center, randomized, double-blind design. That is, the allergen doses on each panel will be randomized into three different configurations, which will be randomly assigned to subjects as they enter the study. Although the investigators and subjects will know which allergen is being tested, they will be blinded to the placement of the allergen doses within each panel. A 48-hour application (approximate) of investigational allergen panel(s), excipient controls and corresponding reference petrolatum (or aqueous) allergen(s) will be applied to the skin of human subjects to test for potential positive allergic responses. Test sites will be evaluated at 3-4, 7-8, 10-14 and 19-23 days after application.

4.8 Primary and Secondary Endpoints	
Primary Endpoint
 
Determination of optimal test allergen dose as:
 
 ▪ The lowest concentration of each dilution series allergen eliciting positive responses in a minimum of 15 subjects. Positive responses are defined as score of 1+, 2+ or 3+ during at least one reaction assessment visit. If a significant number of 3+ responses are elicited, the dose will be selected based on 1+ and 2+ responses. ▪ For all sites with the exception of Germany: Concordance will be measured using Cohen's kappa where less than 0% indicates no agreement, 0-20% indicates poor agreement, 20-40% indicates fair agreement, 40-60% indicates moderate agreement, 60-80% indicates good agreement and 80% or higher indicates very good agreement.

	
Concordance will be measured using all subjects who are tested with each allergen and corresponding reference allergen.
 
Secondary Endpoint
 
Determination of allergen safety:
 
▪ Frequency of tape and polyester chip induced irritation or allergic reactions at Visits 2 through 6.▪ Frequency of subject reported sensations of itching and/or burning for each allergen panel at patch removal.▪ Frequency of positive (1+, 2+, 3+) skin reactions for each investigational and reference allergen dose at each post removal visit and overall.▪ Frequency of negative, doubtful, irritant, late and persistent skin responses for each investigational and reference allergen dose at each post removal visit (late and persistent reactions at visits 4, 5 and 6 only).▪ Frequency of all adverse events. Documentation for all local and systemic adverse reactions classified by the investigator as possibly or definitely related to the study product (e.g., erythema, hyper-pigmentation, hypo-pigmentation, skin thinning or dermatitis flare) will include grade (mild, moderate or severe) and time point (clinic visit). 
Positive results from the common allergen testing will be tabulated in the final report only. No additional analysis will be performed using this data. Comparative data analyses of reactions to these allergens are beyond the scope of this study.

4.9 Subjects	
The study population will consist of subjects with past positive patch test result to at least one of the dilution series metals being tested on this study or strong suspicion of metal contact allergy.
 
A minimum of 15 subjects per dilution series allergen, who exhibit a positive skin response (score of 1+, +2 or 3+ during at least one reaction assessment visit) to the dilution series allergen and/or at least one of its corresponding reference allergens, is needed to complete the study.
 
Subjects with a past positive patch test response to at least one of the dilution series allergens will be tested with the allergen panel and corresponding reference allergen(s) to which they have had the previous response. Subjects with suspicion of metal contact allergy will be tested with all dilution series and reference allergens. All subjects will be tested with the excipient controls. The common allergens will be tested at the discretion of the investigator.

	
The study population should include a reasonable representation of patients who have undergone a metal replacement procedure.

4.10 Justification of Sample Size	
Past dose response study populations have included 20 adult subjects (per allergen) with a historical positive patch test to the corresponding reference allergen. In these studies, determination of the optimal test allergen dose was the lowest concentration eliciting a 1+, 2+ or 3+ positive reaction in 70-90% of subjects with the fewest number of 3+ reactions; therefore a minimum of 14 subjects with positive reactions was needed to determine optimal test allergen dose.
 
Due to the fact that not all of the metals being tested on this study have a large database of patients with past patch-test positive reactions, the inclusion criteria was modified to include subjects with a suspicion of metal allergy, in addition to those with a historical positive patch test. Because it is anticipated that not all subjects will test positive, the study will conclude when a total of 400 subjects have been tested whether or not the 15 positive response subjects per allergen quota is met.
 
The option of further testing may be considered for any allergen that elicits a minimum of 8 positive responses. In such a case, the protocol will be amended

4.11 Investigational Allergen Panels	
Aluminum Dilution Series
 
0.040 mg/cm² aluminum chloride hexahydrate 0.12 mg/cm² aluminum chloride hexahydrate 0.36 mg/cm² aluminum chloride hexahydrate 0.72 mg/cm² aluminum chloride hexahydrate
 
0.047 mg/cm² aluminum lactate 0.14 mg/cm² aluminum lactate 0.42 mg/cm² aluminum lactate 0.84 mg/cm² aluminum lactate
 
Copper Dilution Series
 
0.013 mg/cm² copper sulfate anhydrous 0.040 mg/cm² copper sulfate anhydrous 0.080 mg/cm² copper sulfate anhydrous 0.12 mg/cm² copper sulfate anhydrous

Investigational Allergen Panels (continued)	
Manganese Dilution Series
 
0.013 mg/cm² manganese chloride tetrahydrate 0.040 mg/cm² manganese chloride tetrahydrate 0.080 mg/cm² manganese chloride tetrahydrate 0.24 mg/cm² manganese chloride tetrahydrate
 
Molybdenum Dilution Series
 
0.0067 mg/cm² ammonium molybdate 0.020 mg/cm² ammonium molybdate 0.040 mg/cm² ammonium molybdate 0.12 mg/cm² ammonium molybdate

	
Tin Dilution Series
 
0.018 mg/cm² tin chloride dihydrate 0.037 mg/cm² tin chloride dihydrate 0.11 mg/cm² tin chloride dihydrate 0.33 mg/cm² tin chloride dihydrate
 
Titanium Dilution Series
 
Titanium Citrate
 
Ammonium titanium peroxy citrate (0.055 mg Ti/cm²) Ammonium titanium peroxy citrate (0.11 mg Ti/cm²) Ammonium titanium peroxy citrate (0.22 mg Ti/cm²)
 
Titanium Lactate
 
Ammonium titanium lactate (0.070 mg Ti/cm²) Ammonium titanium lactate (0.14 mg Ti/cm²) Ammonium titanium lactate (0.28 mg Ti/cm²)
 
Titanium Oxide Oxalate
 
Potassium titanium oxide oxalate (0.060 mg Ti/cm²) Potassium titanium oxide oxalate (0.12 mg Ti/cm²) Potassium titanium oxide oxalate (0.24 mg Ti/cm²) Ammonium titanium oxide oxalate (0.055 mg Ti/cm²) Ammonium titanium oxide oxalate (0.11 mg Ti/cm²) Ammonium titanium oxide oxalate (0.22 mg Ti/cm²)

Investigational Allergen Panels (continued)	
Vanadium Dilution Series
 
Vanadium chloride (0.0042 mg V/cm²) Vanadium chloride (0.0083 mg V/cm²) Vanadium chloride (0.025 mg V/cm²) Vanadium chloride (0.050 mg V/cm²)
 
Vanadium oxide sulfate (0.0042 mg V/cm²) Vanadium oxide sulfate (0.0083 mg V/cm²) Vanadium oxide sulfate (0.025 mg V/cm²) Vanadium oxide sulfate (0.050 mg V/cm²)

	
Zinc Dilution Series
 
0.013 mg/cm² zinc chloride 0.040 mg/cm² zinc chloride 0.080 mg/cm² zinc chloride 0.24 mg/cm² zinc chloride
 
The dose per unit area of experimental T.R.U.E. Test allergens is calculated based on the molecular weight of the compound. Exceptions are Titanium and Vanadium allergens as molecular weights are not known for all of these, hence the dose per unit area for Titanium and Vanadium allergens is based only on the metal part of the compound.

	
Common Allergens/ Excipient Controls
 
0.2 mg/cm² nickel sulfate 0.054 mg/cm² potassium dichromate 0.02 mg/cm² cobalt dichloride 0.075 mg/cm² gold sodium thiosulfate (GST) Blank patch Polyvinylpyrrolidone (PVP) Hydroxypropyl cellulose (HPC)

4.12 Reference Allergens	
 ▪ The Aluminum Dilution Series will be tested concurrently with 
 ○ Aluminum chloride hexahydrate, 10 % w/w in petrolatum ○ Aluminum lactate, 12 % w/w in petrolatum ▪ The Copper Dilution Series will be tested concurrently with copper sulfate anhydrous, 2 % w/w in petrolatum ▪ The Manganese Dilution Series will be tested concurrently with manganese chloride tetrahydrate, 2 % w/w in petrolatum ▪ The Molybdenum Dilution Series will be tested concurrently with ammonium molybdate, 1% aqueous solution. ▪ The Tin Dilution Series will be tested concurrently with tin chloride dihydrate, 1% w/w in petrolatum ▪ The Titanium Dilution Series will be tested concurrently with

	
 ○ Ammonium titanium peroxy citrate, 17% w/w in petrolatum ○ Ammonium titanium lactate, 34% aqueous solution ○ Potassium titanium oxide oxalate, 22% w/w in petrolatum ○ Ammonium Titanium oxide oxalate 19% w/w in petrolatum ▪ The Vanadium Dilution Series will be tested concurrently with 
 ○ Vanadium chloride, 1% w/w in petrolatum ○ Vanadium oxide sulfate, 1.5% w/w in petrolatum ▪ The Zinc Dilution Series will be tested concurrently with zinc chloride, 2% w/w in petrolatum 
NOTES: 1) The common allergens (Panel 6) will not be tested against reference allergens. 2) Subjects enrolled in Germany will not be tested with the reference allergens
 
The Finn Chamber, polypropylene-coated, supplied by SmartPractice, will be used to apply the reference allergens. Reference allergens will be dispensed at the rate of 20 μl/chamber using a precision allergen dispenser.

4.13 Study Outline	
After the subject has consented and all inclusion/exclusion criteria are met the subject may be eligible for enrollment. If enrolled, the following timeline will be followed:
 
Clinic Visit 1 Day 0
 
Clinic Visit 2 Day 2
 
Clinic Visit 3 Day 3-4
 
Clinic Visit 4 Day 7-8
 
Clinic Visit 5 Day 10-14
 
A. Investigational allergen panel(s) and the appropriate reference allergen(s) will be applied to the skin on the subject's back. Patch tests are to be worn for approximately 48 hours.
 
B. Adhesion of the investigational allergen panel(s) and the reference allergen(s) will be evaluated. Tape and polyester chip induced site irritation will be scored. Subject reported itching and burning sensations will be captured. Adverse events will be documented.
 
C. Tape and polyester chip induced site irritation will be scored. Skin reactions will be evaluated. Adverse events will be documented. De-identified photographs of site reactions may be taken at the discretion of the Investigator and will not be reviewed or collected by the study sponsor.
 
D. Unresolved tape and or polyester chip induced irritation will be scored. Skin reactions will be evaluated. Late or persistent reactions and adverse events will be documented. De-identified photographs of site reactions may be taken at the discretion of the Investigator and will not be reviewed or collected by the study sponsor.
 
E. Unresolved tape and or polyester chip induced irritation will be scored. Skin reactions will be evaluated. Late or persistent reactions and adverse events will be documented. De-identified photographs of site reactions may be taken at the discretion of the Investigator and will not be reviewed or collected by the study sponsor.

Clinic Visit 6 Day 19-23
	
F. Follow up visit to record unresolved tape or polyester chip induced irritation, late or persistent reactions and documentation of adverse events. Photographs of site reactions may be taken at the discretion of the Investigator. Investigator may elect to perform this evaluation via telephone if no reactions are present.


4.14 Monitored Parameters
	
Visit 1 (Day 0)
 
 ▪ Informed Consent ▪ Documentation of inclusion/exclusion criteria ▪ Completion of Qualification and Type of Metal Exposure Questionnaires ▪ Subject demographics (date of birth, gender and ethnicity) ▪ Concomitant medication use and medical history ▪ Urine pregnancy test (if needed) ▪ Physical examination to record current sites of dermatitis ▪ Application of the investigational allergen panel(s) and reference allergen(s) to the paraspinal region of the upper back. NOTE: Upper arms may be used if there is not adequate space on the back for all panels. 
Visit 2 (Day 2)
 
 ▪ Documentation of adhesion of investigational allergen panel(s) and reference allergen(s) to confirm adequate allergen-to-skin contact ▪ Removal of investigational allergen panel(s) and reference allergen chamber(s) ▪ At least 15-minute wait between patch removal and irritation evaluation. ▪ Evaluation of tape and polyester chip induced irritation. ▪ Documentation of subject self-report of itching and burning sensations at test panel sites ▪ Documentation of subject-reported adverse events, worsening of a pre-existing condition/disease/symptom or changes to concomitant medications. 
Visit 3 (Day 3-4)
 
 ▪ Evaluation of tape and polyester chip induced irritation. ▪ Evaluation of patch site skin reactions ▪ Documentation of subject-reported adverse events, worsening of a pre-existing condition/disease/symptom or changes to concomitant medications. ▪ Photographs of site reactions (taken at the discretion of the Investigator). 
Visit 4 (Day 7-8)
 
 ▪ Evaluation of unresolved tape and or polyester chip induced irritation.

	
 ▪ Evaluation of patch site skin reactions ▪ Categorization of positive reactions as late or persistent ▪ Documentation of subject-reported adverse events, worsening of a pre-existing condition/disease/symptom or changes to concomitant medications. ▪ Photographs of site reactions (taken at the discretion of the Investigator). 
Visit 5 (Day 10-14)
 
 ▪ Evaluation of unresolved tape and or polyester chip induced irritation. ▪ Evaluation of patch site skin reactions ▪ Categorization of positive reactions as late or persistent; ▪ Documentation of subject-reported adverse events, worsening of a pre-existing condition/disease/symptom or changes to concomitant medications. ▪ Photographs of site reactions (taken at the discretion of the Investigator). 
Visit 6 (Day 19-23)
 
 ▪ The investigative site will phone the subject to determine if there are any unresolved reactions from the tape, or at the individual test sites. If the subject reports no remaining reactions the Investigator may choose at this point to complete the visit over the telephone. ▪ If the visit is conducted over the telephone all visit related paperwork including adverse events and/or changes to concomitant medications will be recorded. ▪ Should the Investigator elect to see the subject in the office, the following procedures will be performed: 
 ▪ Evaluation of unresolved tape and or polyester chip induced irritation. ▪ Evaluation of patch site skin reactions. ▪ Categorization of positive reactions as late or persistent. If a persistent, escalating reaction is noted at Visit 6, the investigator will determine if follow up action is warranted. ▪ Subject-reported adverse events, worsening of a pre-existing condition/disease/symptom or changes to concomitant medications will be recorded. ▪ Photographs of site reactions (taken at the discretion of the Investigator). ▪ Following Visit 6 the Investigator will categorize the skin reactions at each site as either negative or positive.
4.15 Data Analysis	The frequency of skin responses; positive (1+, 2+, 3+), negative, doubtful and irritant, will be calculated for each dilution series investigational allergen dose and reference allergen. The optimal

	
allergen dose will be based on the following criteria:
 
▪ The lowest concentration of each dilution series allergen eliciting positive responses in a minimum of 15 subjects. Positive responses are defined as score of 1+, 2+ or 3+ during at least one reaction assessment visit. If a significant number of 3+ responses are elicited, the dose will be selected based on 1+ and 2+ responses.▪ For all sites with the exception of Germany: Concordance will be measured using Cohen's kappa where less than 0% indicates no agreement, 0-20% indicates poor agreement, 20-40% indicates fair agreement, 40-60% indicates moderate agreement, 60-80% indicates good agreement and 80% or higher indicates very good agreement. Concordance will be measured using all subjects who are tested with each allergen and corresponding reference allergen. 
Safety evaluations will be tabulated as follows:
 
▪ Frequency of tape and polyester chip induced irritation or allergic reactions at Visits 2 through 6 for the T.R.U.E. Test tape and polyester chips (Panels 1-6) and Finn Chamber tape (Reference allergen panels).▪ Frequency of subject reported sensations of itching and/or burning for each allergen panel at patch removal.▪ Frequency of positive (1+, 2+, 3+) skin reactions for each investigational and reference allergen dose at each post removal visit and overall.▪ Frequency of negative, doubtful, irritant, late and persistent skin reactions for each investigational and reference allergen dose at each post removal visit (late and persistent reactions at visits 4, 5 and 6 only).▪ Frequency of all adverse events. Documentation for all local and systemic adverse reactions classified by the investigator as possibly or definitely related to the study product (e.g., erythema, hyper-pigmentation, hypo-pigmentation, skin thinning or dermatitis flare) will include grade (mild, moderate or severe) and time point (clinic visit). 
Statistical processing will be performed using SAS® software.

4.16 Study Duration	The proposed study is intended to begin in 2016, no later than 6 months after approval of the final protocol by the IRB or Ethics Committee. Given the rarity of sensitization to these metals, the study may be concluded at an individual site if the Investigator believes that the patient data base has been exhausted. When this maximum number of subjects has been reached the sponsor of the study will inform the investigator that the study has been concluded at that site.

Clinical Evaluation of Metal Panel Allergens:
Aluminum, Copper, Manganese, Molybdenum, Tin, Titanium,
Vanadium and Zinc Dose Response Study

SP 14 8MP 201

	
The duration of participation for each enrolled subject will be approximately three weeks.
 
The final report will be submitted to the Principal Investigator within 120 days of data base lock and to the FDA, European Commission and PMDA within 1 year of study completion.

--	---------------------------------------------------------------------------------------------------------------------------------------------------------------------------------------------------------------------------------------------------------------------------------------------

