- Sensitive subjects (those who have had a past positive patch test to at least one of the dilution series allergens) may be tested with the allergen panels(s) and corresponding reference allergen(s) (with the exception of subjects enrolled in Germany who will not be tested with the reference allergens) to which they have had a previous response.
 - The Investigator will use his or her experience and medical expertise to determine if a subject with a past positive patch result should be tested to all dilution series allergens or only to the allergen to which the subject has had the past response.
 - Subjects with a past positive response to copper, zinc, tin, manganese or molybdenum will be tested with the panel containing the past positive response allergen plus the other allergen(s) located on the same panel. Specifically, Panel 2 contains copper, zinc and tin, and Panel 3 contains manganese and molybdenum. Hence, subjects with a past positive response to one of the allergens on the panel will also be tested with the other allergen(s) located on the same panel. It will not be necessary to test the additional reference allergens.
- Subjects with suspicion of metal contact allergy potentially associated with a metal implant will be tested with all dilution series and reference allergens.
- All subjects will be tested with the excipient controls on Panel 6. The Investigator will use his or her experience and medical expertise to determine if a subject with a strong suspicion of metal contact allergy who has not undergone previous patch testing will benefit from being patch tested with the four common allergens (nickel, chromate, cobalt and gold) in order to provide the individual with a complete diagnosis of metal contact allergy. Should the Investigator decide that testing with the four common allergens will not be of benefit to the subject, the Investigator will cut Panel 6 as illustrated in Figure 9, (Section 11.1, Investigational Allergen Panels) before applying the panel.

10.2 Visit 2: Day 2

Prior to removal of the investigational allergen and reference panels, tape adhesion will be evaluated and scored according to the following adhesion scale:

Excellent:	Skin contact good; all tape edges adherent; all allergens in contact with the skin
Good:	Skin contact acceptable; some tape edges lifting; all allergens in contact with the skin
Poor:	Little to no skin contact with panel; one or more allergens not in contact with the skin

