Detached:	Panel completely off the skin; none of the allergens in contact with the skin

If adhesion is 'Poor' or 'Detached' the allergen sites that were not in contact with the skin at the time of panel removal will be identified.

Patches that do not remain in place (completely detached) for the intended wear period (approximately 48 hours or two days) will not be replaced. The subject will be asked to return for follow-up visits until all patch sites reactions have resolved but data from this subject will not be included in the analysis of positive responses necessary to determine optimal dose.

Subjects whose patches are not worn for the intended wear period may return to be retested after 3 weeks at the discretion of the Investigator providing the skin site remains free of conditions that may affect test results.

Factors such as oily skin, excess hair, wet panel, sweat/skin moisture, and activity-associated failure, which may potentially contribute to poor adhesion, will also be captured on the data collection form.

The patch panels will be removed and time documented. There will be at least a 15-minute wait between patch removal and the irritation evaluations. Following the 15-minute wait, tape sites (entire panel minus the chip sites) then the polyester chip sites will be evaluated for skin irritation.

[figure not shown]
Skin irritation will be documented as follows:

- Panels 1-6: Irritation attributed to the adhesive used to adhere the panels to the skin (tape irritation) will be documented if the site of the entire panel with the exception of the chip sites, as shown below in Figure 5, shows signs of irritation
- Panels 1-6: Irritation attributed to the gel chips will be documented if all chip sites show signs of irritation. Note: To ensure that irritation resulting from skin contact with the polyester chip is not confused with an allergic response to a specific allergen, all of the polyester chip sites must present the same or nearly the same degree of irritation.
 - Panel 1: Chips on positions 1-4 and 7-10 will be evaluated for irritation
 - Panel 2: Chips on positions 1-12 will be evaluated for irritation
 - Panel 3: Chips on positions 1-4 and 7-10 will be evaluated for irritation
 - Panel 4: Chips on positions 1-12 will be evaluated for irritation
 - Panel 5: Chips on positions 1-4 and 7-10 will be evaluated for irritation

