2. Categorize the skin reactions at each site as either negative or positive. No skin reaction scores (1+, 2+ or 3+) assigned to during any of the reaction assessment visits, (Visits 3-6) would constitute a negative reaction. A positive skin reaction is defined as an assigned score of 1+, +2 or 3+ during at least one of the reaction assessment visits (Visits 3-6).

[figure not shown]

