Overall concordance of skin reaction responses from each allergen dose will be compared with reference allergen by using Kappa statistic as described below,

Kappa statistics (K) = $(P_0 - P_e) / (1 - P_e)$

Where P_0 is the relative observed agreement among raters (identical to accuracy), and P_e is the hypothetical probability of chance agreement and the Kappa agreement statistics score is interpreted as,

≤ 0 as indicating no agreement

0.01 – 0.20 as poor agreement

0.21 – 0.40 as fair agreement

0.41 – 0.60 as moderate agreement

0.61 – 0.80 as good agreement

0.81 – 1.00: very good agreement

Concordance will be measured using all subjects who are tested with each allergen and corresponding reference allergen.

Note: Data from the subjects with the completely detached patches for the intended wear period (approximately 48 hours or two days) will not be included in the analysis of positive responses necessary to determine optimal dose.

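### Loss of skin contact is recorded site by site at Visit 2 but used in no analysis rule, so a non-reacting no-contact site on a Poor panel enters kappa and the per-dose percentages as a negative

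*Protocol*

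**What the plan says.** **Purpose of the check.** Protocol 4.14 (Visit 2) lists "Documentation of adhesion of investigational allergen panel(s) and reference allergen(s) to confirm adequate allergen-to-skin contact".

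**What is recorded.** The adhesion scale in Protocol 10.2 defines Poor as "Little to no skin contact with panel; one or more allergens not in contact with the skin" and, as a separate category, Detached as "Panel completely off the skin; none of the allergens in contact with the skin". For either grade, "the allergen sites that were not in contact with the skin at the time of panel removal will be identified". The record is therefore kept by position.

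**What is excluded.** Protocol 10.2 has one adhesion exclusion. It begins "Patches that do not remain in place (completely detached) for the intended wear period" and removes that subject's data from the analysis of positives used to choose the dose. The Note that closes SAP 6.1 repeats it for "Data from the subjects with the completely detached patches for the intended wear period". Neither text mentions Poor panels or the list of no-contact positions.

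**How a site becomes negative.** Protocol 10.6: "No skin reaction scores (1+, 2+ or 3+) assigned to during any of the reaction assessment visits, (Visits 3-6) would constitute a negative reaction". The rule carries no condition on contact.

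**What enters kappa.** Protocol 4.15, repeated in SAP 6.1: "Concordance will be measured using all subjects who are tested with each allergen and corresponding reference allergen". SAP 6.1 drops a subject from concordance only when the investigator's determination is missing for one of the two panels. SAP 3.6 and 3.7 define the FAS and mFAS without any adhesion criterion.

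**The concern.** A patch that was off the skin gives little or no information about whether the subject reacts to that dose. If its blank reading is stored as a negative, an adhesion failure looks the same as a true non-response.

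In a reactive subject, losing contact on one side of the pair turns an agreement on positive into a disagreement. Losing both sides turns it into an agreement on negative. Kappa is labelled Primary Endpoint 02 and is read against named bands, so it could understate agreement for reasons unrelated to dose. The positive percentages per dose and per reference would shrink in the same way, because the denominator keeps sites that had little chance to react.

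**Working it through.** **1. The plan's own figure.** The documents give no contact-failure rate and no expected kappa. The only derived number nearby is the 14 positives carried over from earlier studies (Protocol 12.2): 0.70 × 20 = 14, which reproduces. It bears on the count, not on kappa.

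**2. Following one site through the rules.** Take a chip listed at Visit 2 as off the skin on a Poor panel, with no later 1+ to 3+.
- Protocol 10.2 exclusion: not triggered if detachment means the whole panel, as the adhesion scale has it.
- Protocol 10.6: negative.
- SAP 6.1 missing-determination rule: not triggered, because a determination (negative) exists.
- SAP 3.6 and 3.7: the subject stays in both analysis sets.
- Result: the site counts as negative in kappa and in the dose denominator.

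**3. Direction.** SAP 6.1 gives kappa = (P0 − Pe)/(1 − Pe). Write p1 and p2 for the investigational and reference positive rates, and cov for P(both positive) − p1·p2. If a random share L of investigational sites is lost and counted negative,

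kappa' = 2·cov / [p1(1 − 2·p2) + p2/(1 − L)].

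The denominator grows with L, so kappa falls whenever cov > 0. A numerical check of random one-sided loss found no exception in 99,973 random tables with positive association.

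**4. Size, on assumed inputs.** Assume 300 pairs and 20 true reactors. Each patch detects 80-95% of reactors, with 0.5-1% false positives. Contact is lost at a share q of sites on each side, independently, so every positive probability is multiplied by (1 − q).

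One case in full (detection 0.90, false positives 0.5%):
- No loss: both positive = 20 × 0.90² + 280 × 0.005² = 16.207. Each discordant cell = 20 × 0.90 × 0.10 + 280 × 0.005 × 0.995 = 3.193. Both negative = 277.407. P0 = 0.97871; each positive rate = 19.4/300 = 0.06467; Pe = 0.87903. Kappa = 0.09968/0.12097 = 0.824.
- q = 10%: detection becomes 0.81 and false positives 0.45%. Both positive = 13.128, each discordant cell = 4.332, both negative = 278.208. P0 = 0.97112, Pe = 0.89037. Kappa = 0.08075/0.10963 = 0.737.

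| Detection / false positives | No loss | 1% | 2% | 5% | 10% |
|---|---|---|---|---|---|
| 0.80 / 1% | 0.661 | 0.654 | 0.647 | 0.626 | 0.591 |
| 0.90 / 0.5% | 0.824 | 0.815 | 0.806 | 0.780 | 0.737 |
| 0.95 / 0.5% | 0.877 | 0.867 | 0.858 | 0.830 | 0.783 |

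The drop is 0.007-0.019 at 1-2%, 0.035-0.047 at 5% and 0.070-0.093 at 10%. On the SAP bands, 0.661 to 0.591 goes from good to moderate, and 0.824 to 0.737 from very good to good.

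**5. Other loss patterns, same model.** One-sided loss gives about half the drop: 0.018-0.024 at 5% and 0.037-0.049 at 10%. If both sites of a pair are always lost together, kappa is unchanged or rises by about 0.002 at most. In separate assumed tables at 10% total loss, the joint share had to reach about 86-98% before kappa stopped falling.

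**6. Percentages.** Each positive percentage is multiplied by (1 − q). In the worked case at 10% it goes from 19.4/300 = 6.47% to 17.46/300 = 5.82%.

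**7. Count of 15.** A site that did not react adds nothing to a count of positives, whether it is removed or called negative.

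**The case against.** **No sentence says that no-contact sites are negative.** A reader might infer that the plan expressly orders this. It does not; the result follows from the 10.6 rule and the absence of any exclusion for Poor panels. The word patch often means a single chip (Protocol 6.11 and 11.1), so the detachment exclusion could be read to cover one lifted chip. The adhesion scale points to the whole panel. The ambiguity stands, and is itself a reason to state the rule.

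**The exclusion may already reach kappa.** The SAP 6.1 Note sits at the end of the kappa text, and the protocol lists kappa among the criteria for the optimal dose. Its wording is narrower, so its scope is unclear rather than plainly limited to the count.

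**Such sites are not simply untested.** Contact is judged at removal, so a site that lifted late may have had most of its exposure. This stands, and it is why a sensitivity analysis with observed scores is needed.

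**The detachment exclusion is not harmless to the count.** One might conclude that it makes no difference to the 15 positives. Protocol 10.2 removes the subject's data, so read literally, one detached panel also removes positives on that subject's well-adhered panels. The count can then change.

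**The size is assumed.** Protocol 10.2 names oily skin, hair, moisture and activity as contributors to poor adhesion. These are largely subject-level factors, so full independence is doubtful. The simple standard error, √[P0(1 − P0)/300]/(1 − Pe), is 0.096, 0.069 and 0.056 for the three no-loss rows, larger than the shift at 5%. That limits how visible the bias would be but does not remove it.

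**No decision turns on kappa.** The current text gives labels and no minimum value. This is correct and limits the consequence.

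**Conclusion.** The point holds as a gap in the analysis rules. The plan collects a position-level record of lost contact and never uses it. Under the rules as written, a non-reacting no-contact site on a Poor panel is a negative in kappa and in the per-dose percentages.

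The downward bias in kappa is the expected direction when contact loss is random and not mainly joint across the pair; it is not certain. Its size cannot be read from the documents. It is negligible at 1-2% loss and could shift an agreement label at 5-10% two-sided loss.

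The documents do not support the stronger inference that the choice of dose is thereby wrong: no kappa threshold drives it, and removing a non-reacting site or calling it negative leaves the 15-positive count as it is. The point merits a SAP change because the reported concordance and percentages depend on an unstated rule that is easy to supply.

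**What to change.** In SAP 6.1, with matching text in Protocol 10.2:

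- Treat each position listed at Visit 2 as lacking skin contact, investigational or reference, on a Poor or Detached panel, as not evaluable. Remove it from that dose's or reference's denominator and drop the affected pair from kappa.
- Add a sensitivity analysis that keeps these positions with their observed scores, counting non-reacting ones as negative, since partial exposure is possible.
- State that the detachment exclusion also applies to kappa, and whether it works by site, panel or subject.
- Tabulate the number of no-contact sites by dose and by reference allergen, so that the size of the effect can be judged.

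The cost is a few lines of SAP and protocol text, a filter on data already collected by position, and slightly fewer pairs in kappa.
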